### 7.1.2. Unsolicited Adverse Events

The occurrence of unsolicited AEs, SAEs, AESIs, and new-onset medical conditions will be listed by body system and preferred term for each vaccination arm. Unsolicited AEs will be assessed with the number and proportion of participants experiencing each safety event at any point during the reactogenicity period, along with the associated exact 95% CI. These will be described overall. A participant will be counted only once per PT per reporting period. Unsolicited AEs will also be tabulated by investigator-determined relationship to investigational product and severity for each vaccination group.

### 7.1.3. Clinical Laboratory Data

Clinical laboratory values, including change from baseline, will be summarized by vaccination group. The values will be graded according to DAIDS Table for Grading the Severity of Adult and Pediatric Adverse Events (DAIDS AE Grading Table), Version 2.1 dated July 2017 that is found on the website <https://rsc.niaid.nih.gov/clinical-research-sites/daids-adverse-event-grading-tables>, and, reported as AEs. All other events will be graded according to the scale in Table S7. The case report form for adverse events will reflect only the highest severity for continuous days an event occurred.

#### Table S7: DAIDS Adverse Event Grading Scale

Estimating Severity Grade for Parameters Not Identified in the Grading Table

The functional table below should be used to grade the severity of an AE that is not specifically identified in the grading table. In addition, all deaths related to an AE are to be classified as grade 5.

PARAMETER	GRADE 1 MILD	GRADE 2 MODERATE	GRADE 3 SEVERE	GRADE 4 POTENTIALLY LIFE- THREATENING
Clinical adverse event NOT identified elsewhere in the grading table	Mild symptoms causing no or minimal interference with usual social & functional activities with intervention not indicated	Moderate symptoms causing greater than minimal interference with usual social & functional activities with intervention indicated	Severe symptoms causing inability to perform usual social & functional activities with intervention or hospitalization indicated	Potentially life-threatening symptoms causing inability to perform basic self-care functions with intervention indicated to prevent permanent impairment, persistent disability, or death

Clinical labs will be presented by visit, grade, and vaccination group. Additionally, descriptive summary statistics (mean, SD, median, minimum, maximum) will be presented for each clinical lab. Change from screening summaries will be done for each follow-up visit. For change-from-screening summaries, participants with an undefined change from screening, due to missing data, will be excluded.

Clinical laboratory values will be presented in listings as well.

## 8. IMMUNOGENICITY EVALUATION

### 8.1. Primary Immunogenicity Analyses

All summaries and analysis of immunogenicity data will be presented for the Immunogenicity Population. Humoral and cellular immunogenicity will be assessed primarily through descriptive statistics. Primary immunogenicity endpoints are IgG binding antibodies to g120 and antigen-specific CD4 and CD8 T cell responses.

The magnitude of plasma IgG (antigen-specific) responses will be measured by the endpoint titer at study weeks 0, 2, 4, 6, 8, 10, 24 and 48. Means or Geometric mean titers (GMTs) will be calculated for each group as appropriate based on the distribution, at each visit, and the per-participant peak response across all visits. Additionally, 95% confidence intervals (CI) will be computed using bootstrapping, or alternative methods. Results will be presented as exponentiated GMT and 95% CI. The distributions of GMTs will be compared across all vaccination groups via ANOVA (null hypothesis that the medians across all groups do not differ) at the 5%-statistical significance level, or using the Kruskal-Wallis test if ANOVA assumptions are violated; in the event Kruskal-Wallis testing is implemented the shape and scale uniformity across groups will be assessed for validity and results interpretation. Pairwise comparisons of GMT responses between dose groups at follow-up time points will be evaluated using a two-sided Mann-Whitney U test, with a Bonferroni-Holm step-down for adjusting p-values for multiple comparisons. Where necessary and appropriate, False Discovery Rates (FDR) will be calculated and reported using the Benjamini-Hochberg (BH) method.

The number and percentage of positive IgG responses to binding targets will be presented by vaccination group and visit based on input from the laboratory team. Differences between vaccinations groups will be evaluated using Fisher's exact test, or chi-squared tests.

Durability of IgG response will be assessed for each participant by estimating the decline in  $\log_{10}$  IgG from peak to 6 and 12 months (weeks 24 and 48 respectively) post final vaccination.

Total immune responses over time will be assessed by the positive incremental area under the curve (AUC). An AUC curve will be constructed with raw, unlogged endpoint titers on the y-axis and visit week on the x-axis (week 0 to week 48). AUC will be logged after calculation from raw values. For comparability between participants with different numbers of samples (visits) available, these values will be scaled (normalized) by the week of the last available sample. If no sample is available for visits other than the first and last, no explicit imputation will be done, and the AUC will be calculated based on available samples. Log AUC will be analysed similarly to the visit-by-visit titers and presented as mean AUC and 95% CI.

The magnitude of CD4+ and CD8+ T-cell effector function and polyfunctionality will be evaluated through response by cytokines such as IFN- $\gamma$  and IL2. The frequencies of CD4 or CD8 T cells responding to each test antigen with IFN- $\gamma$  and/or IL2 will be calculated using the following categories: all IFNy+, all IL2+, IFNy and IL2+, IFNy or IL2+. Descriptive statistics will evaluate the distribution of CD4+ and CD8+ responses and polyfunctionality scores by vaccination group and visit. Differences in CD4+ and CD8+ responses between vaccination groups at each visit will be evaluated using Kruskal-Wallis tests, and pair-wise comparisons of

particular visits will be performed with two-sided Mann-Whitney U test, with a Bonferroni-Holm step-down for adjusting p-values for multiple comparisons.

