9.4. Sample size and Power calculation

The safety, reactogenicity, and tolerability of the vaccine regimens are the primary endpoints for this study. The table below demonstrates effect size with a power of 80%, calculated at a variety of sample sizes.

In [Table 11](#), the sample size calculation for the antibody titer (secondary outcome) will be based on the published data from Pitisuttithum P et.al¹⁸. For the analysis of this experiment we plan on observing a single measurement of peak antibody level per participant. Thus, the study is designed around a 1-way ANOVA model. Tukey's method will be used in the pairwise comparison test. In the analysis we looked at the size of the error bars on the peak of the log antibody titer and based upon our visual inspection we assumed that the residual standard deviation is = 0.2. A sample size of approximately 20 participants per arm was selected to provide $\geq 80\%$ power to detect the effect size of ≥ 0.202 between study arms. Statistical significance will be set at $p=0.05$.

[Table 12](#) depicts SAE or AESI rates and associated 95% confidence intervals in each potential grouping of interest given 0-5 participants with observed events. If we were to observe zero events within a single active study group ($n=20$), the upper limit of a 2-sided exact 95% CI would be 13.9% and true events above this could be ruled out at the $\alpha=0.025$ level.

Table 11: Sample size per arm and minimum effect size with 80% power, assuming residual standard deviation of 0.2

Part A: 3 Active Arms		
n per arm	Minimum effect size	Power
5	0.448	0.801
6	0.398	0.801
7	0.362	0.801
8	0.334	0.800
9	0.312	0.800
10	0.294	0.801
11	0.280	0.804
12	0.266	0.802
13	0.254	0.800
14	0.244	0.800
15	0.236	0.803
16	0.228	0.804
17	0.220	0.801
18	0.214	0.803
19	0.208	0.803

Part A: 3 Active Arms		
20	0.202	0.802
21	0.198	0.806
22	0.192	0.801
23	0.188	0.803
24	0.184	0.804
25	0.180	0.803
26	0.176	0.802
27	0.174	0.808

Table 12: Exact 95% Clopper-Pearson CI for the SAE Rate in Each Study Group

Number of Participants with Event	All Active Groups (n=60)	Any Active Group (n=20)	Arm 1 (n=22)	Arms 2 or 3 (n=19)
0	(0%, 4.9%)	(0%, 13.9%)	(0%, 12.7%)	(0%, 14.6%)
1	(<0.1%, 8.9%)	(0.1%, 24.9%)	(0.1%, 22.8%)	(0.1%, 26.0%)
2	(0.4%, 11.5%)	(1.2%, 31.7%)	(1.1%, 29.2%)	(1.3%, 33.1%)
3	(1.0%, 13.9%)	(3.2%, 37.9%)	(2.9%, 34.9%)	(3.3%, 39.6%)
4	(1.8%, 16.2%)	(5.7%, 43.7%)	(5.2%, 40.3%)	(6.0%, 45.5%)
5	(2.8%, 18.4%)	(8.7%, 49.1%)	(7.8%, 45.4%)	(9.1%, 51.2%)

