## 4. INVESTIGATIONAL PLAN

### 4.1. Overall Study Design and Plan

This is a phase I randomized, double-blind clinical trial to optimize ALFQ dosing among healthy adults not living with HIV. A total of 60 participants will be enrolled to one of three arms (N=20 in each arm) with each arm receiving 300 micrograms of A244 and B.63521. In addition, arm 1 will receive 200 micrograms of ALFQ, arm 2 will receive 100 micrograms of ALFQ, and arm 3 will receive 50 micrograms of ALFQ. The safety, reactogenicity, and immunogenicity will then be compared among the three arms to determine the optimal dose of ALFQ.

All vaccinations will be split into 2 half doses which will both be administered intramuscularly (IM) into the same deltoid muscle. Vaccinations will occur at months 0, 1, and 2. The second vaccination will be administered into the contralateral deltoid at study month 1 compared to the first vaccination at study month 0. The third vaccination at study month 2 will be administered into the same deltoid as the first vaccination at study month 0. Participants will be followed for 12 months following the last study vaccination. Table S2 provides a schematic for the study design.

**Table S2:** Study Design

Number of participants (N) = 60		Vaccination schedule in months (days)		
	Number of participants (N)	Month 0 (Day 1)	Month 1 (Day 29)	Month 2 (Day 57)
Arm 1	20	300µg A244	300µg A244	300µg A244
		300µg B.63521	300µg B.63521	300µg B.63521
		200µg ALFQ	200µg ALFQ	200µg ALFQ
Arm 2	20	300µg A244	300µg A244	300µg A244
		300µg B.63521	300µg B.63521	300µg B.63521
		100µg ALFQ	100µg ALFQ	100 µg ALFQ
Arm 3	20	300µg A244	300µg A244	300µg A244
		300µg B.63521	300µg B.63521	300µg B.63521
		50µg ALFQ	50µg ALFQ	50µg ALFQ

The schedule of events is given in Table S3 below, for reference

Table S3: Schedule of Events (SOE)

Visit Number	0	1	2	3	4	5	6	7	8	9	10  /Exit 4	Phone Follow-up #1	Phone Follow-up #2
Visit Type	Screen	V1	Safety & Immun	V2	Safety & Immun	V3	Safety & Immun	MAAE follow-up	MAAE follow-up				
Visit Day	-30 to -3	1	15	29	43	57	58-59	64	71	169	337	365	393
Window			± 3d	± 7d	± 3d	± 7d	± 3d	± 3d	± 3d	± 7d	± 7d	± 7d	± 7d
Visit Week	0	2	4	6	8	8	9	9	10	24	48	52	56
Clinical													
Briefing and Contact Information	X												
Informed Consent	X												
Test of Understanding	X												
Enrollment and Randomization	X												
Vaccination	X			X		X							
Vital Signs and Physical Exam 	X	X	X	X	X	X	X	X	X	X	X	X	X

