## 5. GENERAL STATISTICAL CONSIDERATIONS

### 5.1. General Principles

All continuous variables, with appropriate transformations (e.g., log, square root, or arcsin) applied as necessary, will be summarized using the following descriptive statistics: n (non-missing sample size), mean, standard deviation, median, minimum, and maximum. The frequency and percentages (with the non-missing sample size as the denominator) of observed levels will be reported for all categorical measures. Exact Clopper-Pearson confidence intervals will be computed for binary variables, where applicable. For continuous variables, confidence intervals will be computed based on the t-distribution with  $n-1$  degrees of freedom, where  $n$  denotes the number of observations. If the data are found to be non-normal, and the sample size is insufficient for application of the central limit theorem (which states that in sufficiently large samples, the sample mean is approximately normal), non-parametric bootstrapped confidence intervals may be calculated instead.

In general, all data listings will be sorted by treatment group and participant, and when appropriate by visit number within participant. All summary tables will be structured with a column for each treatment group in the order presented in the protocol and will be annotated with the total population size relevant to that table/treatment group, including any missing observations.

For hypothesis tests of continuous endpoints, an ANOVA will be preferred for global tests and t-tests will be preferred for pairwise tests. If histograms of the analysis data do not appear by visual inspection to be approximately normal, even after appropriate transformations, or if the sample sizes for comparisons groups are too small for the application of the central limit theorem, a Kruskal-Wallis test will be utilized instead of an ANOVA, and a Wilcoxon rank-sum test will be utilized instead of a t-test. For tests of categorical endpoints, a chi-square test or, if cell counts prohibit the use of a chi-square test, a Barnard's test or Fisher's exact test will be used as appropriate.

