### 5.3.2. Immunogenicity Population

The Immunogenicity Population will include all data from randomized who have received at least one vaccination and have the necessary data available to analyze a given endpoint.

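### SAP 8.1 names an unspecified bootstrap first for the IgG GMT confidence intervals, whereas SAP 5.1 sets a t-interval; the usual percentile or BCa bootstrap at n=20 would cover about 93%, not 95%

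*SAP*

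**What the plan says.** SAP 5.1 (General Principles) gives the rule for continuous variables, transformed where needed: "For continuous variables, confidence intervals will be computed based on the t-distribution with" n−1 degrees of freedom. It then gives an exception. "If the data are found to be non-normal, and the sample size is insufficient for application of the central limit theorem", then "non-parametric bootstrapped confidence intervals may be calculated instead". Both conditions must hold, and even then the bootstrap is optional.

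SAP 8.1 (Primary Immunogenicity Analyses) covers means or GMTs of plasma IgG by arm, at each visit and at the per-participant peak. There it says "Additionally, 95% confidence intervals (CI) will be computed using bootstrapping, or alternative methods". It does not refer back to 5.1. It sets no condition and does not name the type of bootstrap, the number of resamples or the alternative. A later paragraph of 8.1 says that log AUC is handled in a similar way to the visit titers and reported as a mean with a 95% interval.

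The planned size is 20 per arm (SAP 4.1). The immunogenicity population in SAP 5.3.2 takes vaccinated participants who "have the necessary data available to analyze a given endpoint", so the number behind an interval at a given visit can be below 20.

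**The concern.** The method that 5.1 keeps as a conditional, optional fallback comes first and unconditionally in 8.1. A programmer working from 5.1 and another working from 8.1 would produce different intervals for the same log-scale mean, and neither section says which governs. Because 8.1 leaves the alternative open, the method could also be settled after the data are seen.

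The choice has a known small-sample consequence. The common percentile bootstrap of a mean in effect uses the variance with divisor n and normal-like quantiles. It therefore lacks the two corrections built into a t-interval, divisor n−1 and t quantiles. At 20 per arm an interval labelled 95% would then be too narrow. At stake is the stated precision of the IgG summaries in SAP Tables 14 and 15.

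**Working it through.** **The plan's own figure.** The documents state no interval width or coverage, so the only figure to reproduce is the power in Protocol Table 11. Inputs: n=20 per arm, three arms, effect 0.202, SD 0.2, two-sided 5%. The protocol says that "the study is designed around a 1-way ANOVA model". With means −0.101, 0 and +0.101, the noncentrality is 20 × 2 × 0.101² / 0.2² = 10.20 on 2 and 57 df, and the power is 0.8017. The stated value is 0.802, so n and SD are understood as the plan uses them.

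**Width and coverage at n=20, by formula.**

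- t-interval half-width: t(0.975, 19) × s/√20 = 2.093 × s/√20.
- Percentile bootstrap half-width, approximately: 1.960 × √(19/20) × s/√20 = 1.910 × s/√20.
- Width ratio: 1.910/2.093 = 0.913, so 8.7% narrower.
- Coverage for normal data: P(|T₁₉| ≤ 1.910) = 92.9%. The interval misses 7.1% of the time instead of 5%.

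The same formulas at other sizes (n=22 is the Arm 1 column in Protocol Table 12):

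| n | width ratio | coverage |
|---|---|---|
| 22 | 0.921 | 93.1% |
| 20 | 0.913 | 92.9% |
| 18 | 0.903 | 92.6% |
| 15 | 0.883 | 92.1% |

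**Check by simulation** (n=20, 2,000 resamples per sample; 4,000 samples for normal data, 3,000 for each two-fold grid). SAP 3.3 puts endpoint titers on a two-fold dilution grid, so both cases were run.

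| log titers | percentile | BCa | studentised | t |
|---|---|---|---|---|
| normal | 92.9% | 92.9% | 95.2% | 95.1% |
| two-fold grid, SD 0.2 | 92.9% | 92.6% | 95.3% | 95.0% |
| two-fold grid, SD 0.5 | 92.4% | 91.8% | 94.2% | 94.6% |

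For normal data the width relative to the t-interval was 0.909 (percentile), 0.914 (BCa) and 1.013 (studentised). Monte Carlo error on a coverage near 93% is √(0.93 × 0.07/4000) = 0.4 percentage points.

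**Effect on a reported GMT.** The SD comes from Protocol 9.4, where "based upon our visual inspection we assumed that the residual standard deviation is = 0.2". The base of the logarithm is not stated there; log10 is assumed.

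- t: 2.093 × 0.2/√20 = 0.0936, so the limits are the GMT multiplied and divided by 10^0.0936 = 1.241.
- Percentile: 1.910 × 0.2/√20 = 0.0854, factor 1.217.
- Each limit moves by 1.241/1.217 = 1.019, about 2%.

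The difference is 0.0082 on the log scale. With natural logs the movement would be e^0.0082, about 0.8%. With an SD of 0.5 on log10 it would be 10^(0.0082 × 2.5), about 5%.

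**Values below the limit of detection.** SAP 3.3 sets them to half the limit. The documents give no fraction. In one illustrative run with 70% of values at that point and n=20, coverage was 90.7% (t), 89.8% (percentile), 93.2% (BCa) and 94.0% (studentised). So t still beats percentile, but t itself falls short, and this is the kind of case the fallback in 5.1 is for.

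**A limit of the studentised form.** A resample made up only of tied values has SD zero. With 17 of 20 values tied, this happens with probability (17/20)^20 = 3.9%, above the 2.5% tail, so one limit becomes infinite. With 16 of 20 it is 1.2%. In the SD 0.2 grid simulation heavily tied samples did this, and the average studentised width was meaningless.

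**The case against.** The strongest reply is that 8.1 allows alternative methods and names no bootstrap type, so the t-interval remains permitted and a studentised bootstrap would meet its nominal level on roughly normal data. An endpoint section may also depart from general principles, and titers on a coarse grid with substituted low values, at 20 per arm, could meet the trigger in 5.1. All of this stands. A reader might infer that the trial's intervals will be 9% too narrow, or that 8.1 rules out the t-interval. The documents support neither reading. What remains is that the choice is left open, and the usual bootstrap forms miss the stated level.

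A reader might also infer that dose selection depends on these intervals. No passage makes them a selection rule. The arms are compared by ANOVA or Kruskal-Wallis and by Holm-adjusted Mann-Whitney tests, which the interval method does not touch. Nor does the bootstrap sentence clearly reach the T-cell results in Table 16: it sits in the IgG paragraph, and the T-cell paragraph names no interval method.

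Finally, it is tempting to say that late visits are much worse. By formula, coverage falls only from 92.9% at n=20 to 92.1% at n=15.

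**Conclusion.** The point holds as a conflict of defaults together with an unnamed method. If a percentile or BCa bootstrap is used with 20 per arm and roughly normal log titers, intervals are about 9% narrower than t-intervals and cover about 93%. This rests on the assumed bootstrap type. Two-fold rounding gives much the same result. With heavy ties at half the detection limit the ranking changes: BCa is then closer to nominal than t.

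The practical effect is modest: about two percentage points of coverage, and about 2% on each GMT limit at SD 0.2 (log10 assumed). The outputs are descriptive summaries of secondary endpoints in a Phase 1 trial whose primary endpoints are safety. It is worth correcting because the correction is short and the better default is already in SAP 5.1.

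**What to change.** In SAP 8.1, replace the bootstrap sentence with wording to this effect: 95% intervals for GMT and log AUC are t-based with n−1 df on the log scale and back-transformed, per SAP 5.1. Where the fallback in 5.1 applies (non-normal data and small n, for example many values at half the detection limit), a studentised bootstrap is used, with the number of resamples and the seed stated, and not a percentile or BCa interval.

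Two details should go with it. First, state how the fallback is triggered, because 5.1 gives no threshold for either condition. Second, state what is reported when ties make the studentised interval unbounded (17 or more of 20 values equal, as may happen at week 0). The proportion above the limit of detection, with the exact interval that 5.1 already prescribes for binary variables, would serve.

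The cost is a few lines of SAP text and no new data. Against a percentile bootstrap, reported intervals become about 10% wider (1/0.913 = 1.096).

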In Arm 1, a total of 14 participants (58.3%) reported at least one mild solicited event, and 7 (29.2%) reported at least one moderate solicited event. Five participants reported moderate systemic events and 3 reported moderate local events. Sixteen participants reported mild injection site pain and 2 reported moderate injection site pain. Eight individuals reported mild myalgia and 1 reported moderate myalgia. Five participants reported mild fatigue and 2 reported moderate fatigue. Clinical safety laboratory assessments demonstrated that 12 participants had mild decreases in hemoglobin 8 days after product administration. (Personal communication with study PI)

In Arm 2, 5 participants experienced Grade 1 solicited reactions, and one participant experienced a Grade 2 muscle pain at the injection site. Grade 1 change in hemoglobin was reported for two participants. One participant had a Grade 1 change in WBC and a Grade 3 absolute neutrophil count which was similar to baseline. (Personal communication with study PI)

ALFQ will also be administered in one additional clinical trial which may initiate prior to the start of RV575. In the upcoming RV546 trial (IND 27011, NCT04658667), participants in arms 3 and 4 will receive a single IM injection of 200 mcg of ALFQ. These ALFQ doses refer to the MPLA/3DPHAD component of ALFQ.

Manufacture of protein-based vaccine antigens can be technically complex and expensive, both of which can limit vaccine supply, particularly in times of high demand during an epidemic.

Optimization to reduce vaccine dosing can help to alleviate these issues. RV 575 will perform a dose de-escalation study of the ALFQ adjuvant to determine the optimal dose for safety and

immunogenicity. Even a similar, rather than superior, immunogenicity of decreased dosing would result in significant cost savings, thereby facilitating scale-up and delivery to populations at greatest need for a preventive HIV vaccine.

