## **5.7. Multiple Comparisons/Multiplicity**

All hypothesis tests will be performed as two-sided at the 5%-level, including planned immunogenicity analysis. Due to the limited sample size and the early phase of the study, adjustment for multiplicity across endpoints will not occur. For individual endpoints that involve a multitude of hypothesis testing (e.g., gene expression), the analysis will be adjusted for multiplicity using the Bonferroni-Holm step-down procedure [3]. Results will be considered on the strength of evidence. P-values  $\leq 0.05$  will be considered statistically significant evidence of a difference or association.

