gp120 A244gD-D11	xx	xx.x (xx.x, xx.x)	xx	xx.x (xx.x, xx.x)	xx	xx.x (xx.x, xx.x)	0.xx
gp120 MNgD- D11	xx	xx.x (xx.x, xx.x)	xx	xx.x (xx.x, xx.x)	xx	xx.x (xx.x, xx.x)	0.xx
[Additional antigens]							

Note: N = Number of participants in the Immunogenicity Population; n = Number of participants with available analysis values ·ANOVA used to compare mean log AUC across all vaccination groups

**Table 15: Immunology Geometric Mean Titers and Associated 95% CIs by Visit, Antigen, and Vaccination Group – [assay name]**

Visit	Antigen	200 µg ALFQ (N=X)		100 µg ALFQ (N=X)		50 µg ALFQ (N=X)		p-value
		n	GMT (95% CI)	n	GMT (95% CI)	n	GMT (95% CI)	
Baseline (Day 0)	gp120A244gD-D11	xx	xx.x (xx.x, xx.x)	xx	xx.x (xx.x, xx.x)	xx	xx.x (xx.x, xx.x)	0.xx
	[Additional antigens]	xx	xx.x (xx.x, xx.x)	xx	xx.x (xx.x, xx.x)	xx	xx.x (xx.x, xx.x)	0.xx
		xx	xx.x (xx.x, xx.x)	xx	xx.x (xx.x, xx.x)	xx	xx.x (xx.x, xx.x)	0.xx
[Additional visits or Peak]		xx	xx.x (xx.x, xx.x)	xx	xx.x (xx.x, xx.x)	Xx	xx.x (xx.x, xx.x)	0.xx

[figure not shown]
**Note:** This will be adapted for assays with continuous analysis values, as appropriate

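### No between-arm GMT or AUC ratio with a confidence interval is planned, so a non-significant test could be taken as similarity between ALFQ doses

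*SAP*

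**What the plan says.** **Purpose.** Protocol 4.1 and SAP 2 and 4.1 say that safety, reactogenicity and immunogenicity are compared across the arms to find the best ALFQ dose. Protocol 2.2.3 adds: "Even a similar, rather than superior, immunogenicity of decreased dosing would result in significant cost savings".

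**Tests.** SAP 8.1 states: "The distributions of GMTs will be compared across all vaccination groups via ANOVA", with Kruskal-Wallis as the fallback. Pairs of arms are compared by Mann-Whitney with Holm adjustment, and response rates by Fisher or chi-square. Protocol 9.6.3 offers t-tests with Holm. SAP 5.7 says "All hypothesis tests will be performed as two-sided at the 5%-level" and counts p-values at or below 0.05 as evidence of a difference. It does not say how to read a larger one.

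**Estimates.** Table 15 is titled "Immunology Geometric Mean Titers and Associated 95% CIs by Visit, Antigen, and Vaccination Group". Tables 14 to 16 share one layout: an estimate and 95% CI for each arm, then a p-value. No table has a between-arm ratio or difference with an interval.

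**Related text.** The AUC part of SAP 5.6.1 mentions adjusting for equivalence, only within the Kruskal-Wallis fallback of the interim analysis. SAP 8.3 allows Bayes factors in sensitivity analyses, and SAP 11.1 lists them for the interim analysis as appropriate. None of these has a margin, prior or threshold.

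**The concern.** The trial has two questions about dose: do the arms differ, and if a lower dose does no worse, how confident can one be of that? The planned tests answer the first. The second needs an effect estimate with its uncertainty, and the plan has no such output. A team looking at Table 15 would see three GMTs and a p-value. If that p-value exceeded 0.05, the easiest summary would be that the doses gave similar responses, although the data might still be compatible with an appreciable loss at the lower dose. SAP 5.6 says interim immunogenicity results will inform the design of a later trial, so a loose reading could carry forward.

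**Working it through.** **Inputs.** Three arms of 20 (Protocol 9.4: "A sample size of approximately 20 participants per arm was selected to provide" at least 80% power). Two-sided alpha 0.05 (SAP 5.7). Residual SD 0.2 on the log titer scale (Protocol 9.4: "based upon our visual inspection we assumed that the residual standard deviation is = 0.2"). Design difference 0.202. Assumptions: log10 scale (the sample-size section says only log; SAP 8.1 uses log10 for durability), normal errors and no dropout.

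**Step 1: reproduce the plan's figure.** For a one-way ANOVA with range d between the extreme arms, the noncentrality is λ = n Σ(μᵢ − μ̄)² / SD². With the middle arm at the midpoint, Σ = d²/2, so λ = 10 d²/SD². With it equal to either extreme, Σ = 2d²/3, so λ = 13.33 d²/SD². The critical F on 2 and 57 df is 3.159.

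With d = 0.202, SD = 0.2 and the middle arm at the midpoint, λ = 10 × 0.0408/0.04 = 10.20 and power is 0.8017. Protocol Table 11 gives 0.802. This is power to detect a difference.

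**Step 2: chance of a non-significant ANOVA when 50 µg is truly worse than 200 µg.** Each range runs from the middle arm at an extreme (lower figure) to the midpoint (higher figure).

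| True deficit (log10) | GMT lower by | SD 0.2 (planned) | SD 0.3 (assumed) | SD 0.4 (assumed) |
|---|---|---|---|---|
| 0.15 | 29% | 34–47% | 66–74% | 80–84% |
| 0.202 | 37% | 9–20% | 44–56% | 66–73% |
| 0.301 | 50% | 0.1–1% | 10–20% | 33–47% |

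Example: d = 0.15 at SD 0.2 gives λ = 5.625 (midpoint) or 7.5 (extreme), so the chance of non-significance is 0.468 or 0.337. GMT loss is 1 − 10^(−0.15) = 29%.

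The planned 50 vs 200 µg Mann-Whitney test with Holm over three pairs misses more often. In a 5,000-run simulation at SD 0.2 with equally spaced arms, it was non-significant in 57% of trials at a deficit of 0.15 and 28% at 0.202.

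**Step 3: what a ratio interval would show.** The half-width of the 95% CI for a between-arm difference is t(0.975, 57) × SD × √(2/20), with t = 2.002.

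- SD 0.2: 2.002 × 0.2 × 0.3162 = 0.127. With equal observed GMTs the lower limit of the ratio is 10^(−0.127) = 0.747, so losses above about 25% are excluded.
- SD 0.4: 2.002 × 0.4 × 0.3162 = 0.253. The lower limit is 10^(−0.253) = 0.558, so only losses above about 44% are excluded.

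Both cases could come with the same non-significant p-value. The interval separates them.

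**Step 4: can a reader recover the interval from the planned tables?** Roughly. At SD 0.2 the per-arm half-width is t(0.975, 19) × 0.2/√20 = 2.093 × 0.0447 = 0.094. Combining two arms gives 0.094 × √2 = 0.132, against 0.127 from the pooled ANOVA.

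**The case against.** The strongest reply has four parts.

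- **No decision rule is stated.** A reader might infer that the plan prefers a lower dose whenever p exceeds 0.05. The documents do not say this. Protocol 2.2.3 names a cost benefit, and no section sets a selection rule or equates non-significance with similarity. This stands: the issue is what the planned output invites.
- **Non-significance is not the usual outcome at the planned SD.** A reader might also infer that the ANOVA will probably miss a clearly worse dose. At SD 0.2 it misses a 0.15 deficit in fewer than half of trials, a 0.202 deficit in 9–20% and a halving in about 1% or less. The 0.15 deficit is half of one two-fold titer step (0.301 log10; SAP 3.3 has titers in two-fold steps) and below the design difference. This stands too. The larger figures need SDs of 0.3 or 0.4, which are assumptions, although 0.2 was itself read by eye from published error bars.
- **The study is exploratory and descriptive, and per-arm intervals allow an approximate ratio interval.** Both are true, so this is largely a gap in presentation. But an effect estimate with an interval is itself descriptive output, and leaving readers to build it from per-arm bootstrap intervals is unnecessary.
- **Equivalence and Bayes factors are mentioned.** They are, so it would be wrong to say that the plan contains nothing but difference tests. Without a margin, prior or threshold, none of them can support a statement about similarity.

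**Conclusion.** The gap is real and modest. The plan treats similar immunogenicity at a reduced dose as useful, yet specifies no output that quantifies similarity, so a non-significant test could be taken as such. For a 29% lower GMT at 50 µg the ANOVA would be non-significant in 34–47% of trials at SD 0.2, rising to 80–84% if the SD were 0.4. At the design difference and SD 0.2 the figure is 9–20%. These results assume the log10 scale, normal errors, 20 evaluable participants per arm and, above 0.2, SDs that the documents do not give. The sample size is not shown to be wrong, and no formal non-inferiority test is required. This is a cheap reporting improvement.

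**What to change.** 1. In SAP 8.1 and Tables 14 and 15, add the peak-titer GMT ratio and the AUC ratio for 100 vs 200 µg and 50 vs 200 µg, each with a two-sided 95% CI. Take these from the ANOVA on log10 values, or from the bootstrap if its assumptions fail. SAP 8.1 already logs the AUC after calculation, so a difference in mean log AUC back-transforms to a ratio.
2. State in SAP 8.1 that p>0.05 is not evidence of similarity, and that any statement about similarity will report the largest loss the interval does not exclude. With equal observed GMTs this would be about 25% at SD 0.2 and about 44% at SD 0.4.
3. In SAP 5.6.1, define the equivalence adjustment (hypothesis, margin and method) or delete the phrase.

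The cost is two extra columns in existing tables and a few sentences, with no new data or participants. The intervals may prove wide, which would itself be worth reporting.
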